10.55 Case Report Forms - Academic and Community Cancer Research United (ACCRU)

Submit the following AEs not specified in Section 10.5 (paper or electronic, as applicable)

10.551 Grade 2 AEs deemed *possibly, probably, or definitely* related to the study treatment or procedure.

10.552 Grade 3 and 4 AEs regardless of attribution to the study treatment or procedure.

10.553 Grade 5 AEs (Deaths)

10.5531 Any death within 100 days of the patient's last study treatment or procedure regardless of attribution to the study treatment or procedure.

10.5532 Any death more than 100 days after the patient's last study treatment or procedure that is felt to be at least possibly treatment related must also be submitted as a Grade 5 AE, with a CTCAE type and attribution assigned.

10.56 Late Occurring Adverse Events

Refer to the instructions in the Forms Packet (or electronic data entry screens, as applicable) regarding the submission of late occurring AEs following completion of the Active Monitoring Phase (i.e., compliance with Test Schedule in Section 4.0).

11.0 Treatment Evaluation

Lugano Classification Response Criteria

11.1 Response Considerations

Schedule of Evaluations: PET/CT scans are required at baseline for all patients. In addition to a baseline PET/CT scan, confirmatory scans should also be obtained post cycle 2 of chemotherapy and 6-8 weeks post cycle 8 of chemotherapy. During observation, CT scan should be obtained every 3 months during the first year to evaluate for disease progression.

Definitions for clinical response for patients with lymphoma are from the recently revised Cheson's et al criteria published in 2014, derived from the original criteria published in 2007. (Cheson et al, 2014)(Cheson et al, 2007). Up to six of the largest target nodes, nodal masses, or other lymphomatous lesions that are measurable in two diameters (longest diameter [LDi] and shortest diameter) should be identified from different body regions representative of the patient's overall disease burden and include mediastinal and retroperitoneal disease, if involved. A measurable node must have an LDi greater than 1.5 cm. Measurable extranodal disease (eg, hepatic nodules) may be included in the six representative, measured lesions. A measurable extranodal lesion should have an LDi greater than 1.0 cm. Lymph node measurements should be taken from the CT portion of the PET/CT, or other dedicated CT scans where applicable. Measurement of lymphadenopathy for purposes of assessing for PR will be determined by adding the sum of the products of the maximal perpendicular diameters of measured lesions (SPD). The PPD of a single node is sufficient to evaluate for PD (see Table 11.2). Measurable extranodal disease should be assessed in a manner similar to that for nodal disease. For these recommendations, the spleen is considered nodal disease. Disease that is only assessable (eg, pleural effusions, bone lesions) will be recorded as present or absent only, unless, while an abnormality is still noted by imaging studies or physical examination, it is found to be histologically and pathologically negative.

Response is based on PET/CT based on the revised 2014 Lugano Classification. (Cheson et al, 2014).

Progressive disease is based on either PET-CT based (PMD) or CT based (PD) response criteria. PET confirmation of progressive disease is per physician discretion.

11.2 Lugano Classification Response criteria (Cheson et al, 2014)

	PET-CT Based Response	CT-Based Response
Complete Response	Complete metabolic response (CMR)	Complete radiologic response (CR) (all of the following)
Lymph nodes and extralymphatic sites	Score 1, 2, or 3* with or without a residual mass on 5PS† It is recognized that in Waldeyer's ring or extranodal sites with high physiologic uptake or with activation within spleen or marrow (eg, with chemotherapy or myeloid colony-stimulating factors), uptake may be greater than normal mediastinum and/or liver. In this circumstance, complete metabolic response may be inferred if uptake at sites of initial involvement is no greater than surrounding normal tissue even if the tissue has high physiologic uptake	Individual target nodes/nodal masses must regress to ≤ 1.5 cm in LDi No extralymphatic sites of disease
Nonmeasured lesion	Not applicable	Absent
Organ enlargement	Not applicable	Regress to normal
New lesions	None	None
Bone marrow	No evidence of FDG-avid disease in marrow	Normal by morphology; if indeterminate, IHC negative
Partial Response	Partial metabolic response (PMR)	Partial remission (PR) (all of the following)
Lymph nodes and extralymphatic sites	Score 4 or 5† with reduced uptake compared with baseline and residual mass(es) of any size At interim, these findings suggest responding disease At end of treatment, these findings indicate residual disease	$\geq 50\%$ decrease in SPD of up to 6 target measurable nodes and extranodal sites When a lesion is too small to measure on CT, assign 5 mm X 5 mm as the default value When no longer visible, 0 X 0 mm For a node > 5 mm X 5 mm, but smaller than normal, use actual measurement for calculation
Nonmeasured lesions	Not applicable	Absent/normal, regressed, but no increase
Organ enlargement	Not applicable	Spleen must have regressed by $> 50\%$ in length beyond normal
New lesions	None	None
Bone marrow	Residual uptake higher than uptake in normal marrow but but reduced compared with baseline (diffuse uptake compatible with reactive changes from chemotherapy allowed). If there are persistent focal changes in the marrow in the context of a nodal response, consideration should be given to further evaluation with MRI or biopsy or an interval scan	Not Applicable
No Response or Stable Disease	No metabolic response (NMR)	Stable disease (SD)

Target nodes/nodal masses, extranodal lesions	Score 4 or 5 with no significant change in FDG uptake from baseline at interim or end of treatment	< 50% decrease from baseline in SPD of up to 6 dominant, measurable nodes and extranodal sites; no criteria for progressive disease are met
Nonmeasured lesions	Not applicable	No increase consistent with progression
Organ enlargement	Not applicable	No increase consistent with progression
New lesions	None	None
Bone marrow	No change from baseline	Not Applicable
Progressive disease	Progressive metabolic disease (PMD)	Progressive disease (PD) requires at least 1 of the following
Individual target nodes/nodal masses	Score 4 or 5 with an increase in intensity of uptake from baseline and/or	PPD progression: An individual node/lesion must be abnormal with: LDi > 1.5 cm and Increase by $\geq 50\%$ from PPD nadir and An increase in LDi or SDi from nadir 0.5 cm for lesions ≤ 2 cm 1.0 cm for lesions > 2 cm In the setting of splenomegaly, the splenic length must increase by $> 50\%$ of the extent of its prior increase beyond baseline (eg, a 15-cm spleen must increase to > 16 cm). If no prior splenomegaly, must increase by at least 2 cm from baseline New or recurrent splenomegaly
Extranodal lesions	New FDG-avid foci consistent with lymphoma at interim or end-of-treatment assessment	
Nonmeasured lesions	None	New or clear progression of preexisting nonmeasured lesions
New lesions	New FDG-avid foci consistent with lymphoma rather than another etiology (eg, infection, inflammation). If uncertain regarding etiology of new lesions, biopsy or interval scan may be considered	Regrowth of previously resolved lesions A new node > 1.5 cm in any axis A new extranodal site > 1.0 cm in any axis; if < 1.0 cm in any axis, its presence must be unequivocal and must be attributable to lymphoma Assessable disease of any size unequivocally attributable to lymphoma
Bone marrow	New or recurrent FDG-avid foci	New or recurrent involvement

Abbreviations: 5PS, 5-point scale; CT, computed tomography; FDG, fluorodeoxyglucose; IHC, immunohistochemistry; LDi, longest transverse diameter of a lesion; MRI, magnetic resonance imaging; PET, positron emission tomography; PPD, cross product of the LDi and perpendicular diameter; SDi, shortest axis perpendicular to the LDi; SPD, sum of the product of the perpendicular diameters for multiple lesions.

*A score of 3 in many patients indicates a good prognosis with standard treatment, especially if at the time of an interim scan. However, in trials involving PET where de-escalation is investigated, it may be preferable to

consider a score of 3 as inadequate response (to avoid undertreatment). Measured dominant lesions: Up to six of the largest dominant nodes, nodal masses, and extranodal lesions selected to be clearly measurable in two diameters. A measurable node must have an LDi greater than 1.5 cm. Measurable extranodal disease (eg, hepatic nodules) may be included in the six representative, measured lesions. A measurable extranodal lesion should have an LDi greater than 1.0 cm. Nodes should preferably be from disparate regions of the body and should include, where applicable, mediastinal and retroperitoneal areas. Non-nodal lesions include those in solid organs (eg, liver, spleen, kidneys, lungs), GI involvement, cutaneous lesions, or those noted on palpation. Nonmeasured lesions: Any disease not selected as measured, dominant disease and truly assessable disease should be considered not measured. These sites include any nodes, nodal masses, and extranodal sites not selected as dominant or measurable or that do not meet the requirements for measurability but are still considered abnormal, as well as truly assessable disease, which is any site of suspected disease that would be difficult to follow quantitatively with measurement, including pleural effusions, ascites, bone lesions, leptomeningeal disease, abdominal masses, and other lesions that cannot be confirmed and followed by imaging. In Waldeyer's ring or in extranodal sites (eg, GI tract, liver, bone marrow), FDG uptake may be greater than in the mediastinum with complete metabolic response, but should be no higher than surrounding normal physiologic uptake (eg, with marrow activation as a result of chemotherapy or myeloid growth factors).

†PET Deauville 5PS: 1, no uptake above background; 2, uptake \leq mediastinum; 3, uptake $>$ mediastinum but \leq liver; 4, uptake moderately $>$ liver; 5, uptake markedly higher than liver and/or new lesions; X, new areas of uptake unlikely to be related to lymphoma.

12.0 Descriptive Factors

- 12.1 Group: Age \geq 60 years old vs. Age $<$ 60 years old and unable to receive standard ABVD chemotherapy

13.0 Treatment/Follow-up Decision at Evaluation of Patient

- 13.1 Patients will be evaluated for response after 2 cycles of treatment. Patients who are NMR or PMD after 2 cycles of treatment will discontinue treatment and go to the event-monitoring phase per Section 18.0. Patients who are CMR or PMR will continue treatment per protocol.
- 13.2 Patients who develop progressive disease by either PET-CT based (PMD) or CT based (PD) response criteria (see Section 11.0) at any time while receiving therapy or during observation will go to the event-monitoring phase per Section 18.0.
- 13.3 Patients who go off protocol treatment for unacceptable adverse events, subsequent treatment or refusal will go to the event-monitoring phase per Section 18.0.
- 13.4 Observation: The patient will be observed every 30 days x90 days then every 90 days x 2.5 years, then every 6 months until 5 years from registration. If the patient develops disease progression (see section 13.2) or receives subsequent treatment before disease progression while in observation, they will go directly to the event monitoring phase per section 18.0.
- 13.5 Patients who achieve a PMR or CMR will receive a maximum total of 8 cycles of treatment. After 8 cycles, they go to observation per Section 13.4 above.
- 13.6 Early Safety Analysis Phase Only: If a patient fails to complete the first cycle (21 days) of treatment for reasons other than toxicity, the patient will be regarded as in evaluable and will be replaced.

- 13.7 A patient is deemed *ineligible* if after registration, it is determined that at the time of registration, the patient did not satisfy each and every eligibility criteria for study entry. The patient may continue treatment off-protocol at the discretion of the physician as long as there are no safety concerns, and the patient was properly registered. The patient will go directly to the event-monitoring phase of the study (or off study, if applicable).
- If the patient received treatment, all data up until the point of confirmation of ineligibility must be submitted. Event monitoring will be required per Section 18.0 of the protocol.
 - If the patient never received treatment, on-study material and the End of Active Treatment/Cancel Notification Form must be submitted. No further data submission is necessary.
- 13.8 A patient is deemed a *major violation*, if protocol requirements regarding treatment in cycle 1 of the initial therapy are severely violated that evaluability for primary end point is questionable. All data up until the point of confirmation of a major violation must be submitted. The patient will go directly to the event-monitoring phase of the study. The patient may continue treatment off-protocol at the discretion of the physician as long as there are no safety concerns, and the patient was properly registered. Event monitoring will be required per Section 18.0 of the protocol.
- 13.9 A patient is deemed a *cancel* if he/she is removed from the study for any reason before any study treatment is given. On-study material and the End of Active Treatment/Cancel Notification Form must be submitted. No further data submission is necessary.

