16.0 Statistical Considerations and Methodology

16.1 Overview

This is a phase II study of nivolumab and brentuximab vedotin in patients with untreated Hodgkin lymphoma ≥ 60 years old or under 60 and unable to receive standard ABVD chemotherapy. The study is designed to assess the overall metabolic response rate using a single stage phase II study design with an interim analysis. Accrual will be halted after 6 patients to assess safety (see Section 16.4). We do not plan to halt accrual during the interim analysis (see Section 16.214).

16.11 Primary Endpoint: The primary endpoint of this trial is the rate of overall metabolic response. A metabolic response is defined as a patient who has achieved an objective status of PMR or CMR at the end of cycle 8. Throughout Section 16.0, metabolic response will be considered synonymous with “success”, unless specified otherwise. All patients meeting the eligibility criteria, who have signed a consent form and have begun treatment will be evaluable for response, unless they are determined to be a major violation or are replaced in the safety analysis phase per Section 13.6. If the safety analysis determines that a reduction to the starting dose is warranted, only patients treated at the final dose level will be included when evaluating the decision rules in Sections 16.211 and 16.212. Patients treated at other dose levels will be summarized separately.

16.2 Statistical Design:

16.21 Decision Rule:

In a single-agent front-line phase II study of HL patients ≥ 60 years-old treated with brentuximab vendotin, the interim analysis of 27 patients reported rate of 93%⁶. This study will look at responses maintained until the end of cycle 8 and will utilize an updated response criteria that assesses metabolic response (Cheson 2014). Considering these factors, along with heterogeneity of disease in patients with HL and a broader eligibility criteria that includes patients < 60 years old with other co-morbidities, an overall metabolic response rate of greater than 65% for brentuximab vendotin with the addition of nivolumab would be of interest for this study.

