The largest success proportion where the proposed treatment regimen would be considered ineffective in this population is 65%, and the smallest success proportion that would warrant subsequent studies with the proposed regimen in this patient population is 80%. The following one-stage design with an interim analysis is based on a two-stage Simon optimum design and requires 56 evaluable patients to test the null hypothesis that the true success proportion in this patient population is at most 65%.

16.211 Interim Analysis: Enter 25 evaluable patients into the study. If 17 or fewer successes are observed in the first 25 evaluable patients, we will consider this regimen ineffective in this patient population and terminate the study. Otherwise, if the number of successes is at least 18, we will continue accrual.

16.212 Final Decision Rule: Enter an additional 31 evaluable patients into the study. If 40 or fewer successes are observed in the first 56 evaluable patients, we will consider this regimen ineffective in this patient population and terminate this study. Otherwise, if the number of successes is at least 41, this will be considered evidence of promising activity and the treatment may be recommended for further testing in subsequent studies in this population.

16.213 Over Accrual: If more than the target number of patients are accrued, the additional patients will not be used to evaluate the stopping rule or used in any decision making process. Analyses involving over accrued patients are discussed in Section 16.313.

16.214 NOTE: We will not suspend accrual at the interim analysis to allow the first 25 patients to become evaluable, unless undue toxicity is observed. Given the limited

overall sample size and the inclusion of an adverse events stopping rule, we feel it is ethical to not halt accrual for the interim analysis. However, if accrual is extremely rapid, we may temporarily suspend accrual in order to obtain safety data on these patients before re-opening accrual to further patients.

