16.3 Analysis Plan

The analysis for this trial will commence at planned time points (see 16.2) and at the time the patients have become evaluable for the primary endpoint. The Statistician and Study Chair will make the decision, in accord with ACCRU Standard Operating Procedures, availability of data for secondary endpoints (e.g., laboratory correlates), and the level of data maturity. It is anticipated that the earliest date in which the results will be made available via manuscript, abstract, or presentation format is when last patient has been followed for at least 6 months.

16.31 Primary Outcome Analyses:

- 16.311 **Definition:** The primary endpoint of this trial is the rate of overall metabolic response. A metabolic response is defined as a patient who has achieved an objective status of PMR or CMR at the end of cycle 8. All patients meeting the eligibility criteria who have signed a consent form and have begun treatment will

be evaluable for metabolic response, unless they are determined to be a major violation or are replaced in the safety analysis phase per Section 13.6. If the safety analysis determines that a reduction to the starting dose is warranted, only patients treated at the final dose level will be included when evaluating the decision rules in Sections 16.211 and 16.212. Patients treated at other dose levels will be summarized separately.

- 16.312 Estimation: The proportion of successes will be estimated by the number of successes divided by the total number of evaluable patients. Ninety-five percent confidence intervals for the true success proportion will be calculated according to the approach of Duffy and Santner.
- 16.313 Over Accrual: If more than the target number of patients are accrued, the additional patients will not be used to evaluate the stopping rule or used in any decision making processes; however, they will be included in final point estimates and confidence intervals.
- 16.32 Secondary Outcome Analyses
- 16.321 The complete metabolic response rate will be estimated by the total number of complete metabolic responses (CMR) divided by the total number of evaluable patients. All evaluable patients will be used for this analysis. Exact binomial 95% confidence intervals for the true complete metabolic response rate will be calculated.

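### The lead-in replacement rule for DLT counting also removes early non-toxicity dropouts from the primary response denominator, a small upward bias confined to six places

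*Combined protocol and SAP*

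**What the plan says.** Section 13.6 covers the early safety phase and nothing later. When someone in it "fails to complete the first cycle (21 days) of treatment for reasons other than toxicity, the patient will be regarded as in evaluable"; a replacement is then enrolled.

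Section 16.11 makes eligible, consented and treated patients evaluable for response, "unless they are determined to be a major violation or are replaced in the safety analysis phase per Section 13.6". Section 16.311 repeats this in the analysis plan: such patients are "evaluable for metabolic response, unless they are determined to be a major violation or are replaced in the safety analysis phase per Section 13.6".

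That evaluable set is used in four places:
- the interim rule in 16.211: "If 17 or fewer successes are observed in the first 25 evaluable patients", the study stops;
- the final rule in 16.212: "If 40 or fewer successes are observed in the first 56 evaluable patients", the regimen is called ineffective;
- the estimate in 16.312: "The proportion of successes will be estimated by the number of successes divided by the total number of evaluable patients";
- the complete metabolic response rate in 16.321: "All evaluable patients will be used for this analysis".

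Success means PMR or CMR at the end of cycle 8. Only patients at the final dose level enter the decision rules, so one cohort of six lead-in places is concerned. Section 16.22 budgets for two extra safety-analysis patients and names replacement as one reason for extra accrual.

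**The concern.** Replacing a patient who was not observed for a full cycle is sensible when DLTs are counted. It is a different matter for response. Reasons other than toxicity are not limited to administrative loss; they include progression, death from lymphoma and refusal. Section 13.2 sends patients with progression to event monitoring, and 13.3 does the same for refusal: "Patients who go off protocol treatment for unacceptable adverse events, subsequent treatment or refusal will go to the event-monitoring phase per Section 18.0". Such a patient is almost certainly a non-success at the end of cycle 8. It is not fully certain, because 13.6 does not itself say that the patient leaves treatment.

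The plan therefore treats the same event in two ways. In the lead-in the patient is removed; after the lead-in the patient stays in the denominator, unless ruled a major violation. In a single-arm trial decided by a count of successes, removing likely failures raises the response rate, lowers the chance of stopping at the interim and raises the false-positive rate. PFS and OS are not affected by this wording.

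**Working it through.** **Inputs.** From 16.2: null rate 65%, target rate 80%; continue if at least 18/25; declare activity if at least 41/56. From 16.4: six evaluable lead-in patients per dose level. The documents give no rate of cycle-1 loss for non-toxicity reasons, so 1%, 2% and 5% are assumptions, with 5% as the high end.

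**Step 1: reproduce the plan's table (16.24).** P(declare) is the sum over x = 18 to 25 of P(X1 = x) × P(X2 ≥ 41 − x), with X1 ~ Bin(25, p) and X2 ~ Bin(31, p). P(stop) = P(X1 ≤ 17).

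| True rate | 0.65 | 0.70 | 0.75 | 0.80 |
|---|---|---|---|---|
| P(declare) | 0.0973 | 0.2932 | 0.5932 | 0.8525 |
| P(stop) | 0.6939 | 0.4882 | 0.2735 | 0.1091 |

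All eight entries agree with the plan at two decimals.

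**Step 2: current wording.** Let q be the chance that a lead-in patient is removed and r the chance that a removed patient would have been a success. Hold the success rate in all treated patients at p. The six kept lead-in patients then respond at (p − q·r)/(1 − q), and the other 19 + 31 at p. At p = 0.65:

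| q | Kept rate, r = 0 | P(declare), r = 0 | P(stop), r = 0 | P(declare), r = 0.25 | P(stop), r = 0.25 | P(at least one removal) = 1 − (1 − q)^6 |
|---|---|---|---|---|---|---|
| 0 | 0.6500 | 0.0973 | 0.6939 | 0.0973 | 0.6939 | 0 |
| 1% | 0.6566 | 0.0995 | 0.6881 | 0.0986 | 0.6903 | 0.0585 |
| 2% | 0.6633 | 0.1017 | 0.6821 | 0.1000 | 0.6867 | 0.1142 |
| 5% | 0.6842 | 0.1091 | 0.6631 | 0.1044 | 0.6751 | 0.2649 |

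At r = 0.65 the figures stay at 0.0973 and 0.6939 for every q: the bias vanishes only if removed patients would have responded as often as the rest. At q = 5% and r = 0 the expected rate among the 56 is (6 × 0.6842 + 50 × 0.65)/56 = 65.4%.

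**Step 3: one removal at a cut-off.** If the removed patient is put back as a non-success, the last-counted patient moves out. A result of 18/25 becomes 17/25 (stop) if the 25th patient was a success. The probability is 18/25 = 0.72 at q = 0 and 0.717 at q = 2%. A result of 41/56 becomes 40/56 (not promising) with probability 0.704 at q = 0 and 0.703 at q = 2%. As plain all-treated proportions, 18/26 is 69.2% and 41/57 is 71.9%; these are descriptive only.

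**Step 4: effect of the fix.** Take q = 2% and r = 0. In a trial with exactly one removal, the first 25 are one non-success, six kept patients and 18 others.

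| P(declare), q = 2% | Current wording | Fix, exactly one removal | Fix, averaged over all trials |
|---|---|---|---|
| True 65% | 0.102 | 0.064 | 0.097 |
| True 80% | 0.863 | 0.779 | 0.853 |

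The averages return to the Step 1 values because every treated patient then counts and succeeds with probability p.

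All figures ignore the separate ineligibility and major-violation exclusions.

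**The case against.** The exclusion is stated in advance, identically in two sections, and is budgeted for. It depends on completing 21 days, not on a response reading; the first scheduled response scan comes after cycle 2, and toxicity failures stay in the denominator. At 1% and 2% removal the false-positive rate still rounds to the stated 0.10. The boundary probabilities need both a removal and a result exactly on the cut-off. At 2% removal and a true 65%, the chance of an interim reversal is about 0.114 × 0.136 × 0.717 = 1.1%, where 0.136 is the chance of exactly 18/25. The net change in final declarations is 0.1017 − 0.0973 = 0.0044.

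All of this stands as a limit on size. It does not make the exclusion neutral, since early progression, death and refusal go with non-response, and stating a rule in advance does not remove a bias.

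A second objection concerns the scale. If the kept lead-in patients respond at the same rate as everyone else, there is no false-positive inflation now, and the fix lowers power at 80% to about 0.84 at 2% removal. The arithmetic is right, but the premise is uneven. Later patients' early failures already count within their 80%, whereas the treated lead-in patients would then respond at only 0.98 × 80% = 78.4%. The claim that power of 0.85 is kept therefore rests on holding the all-treated rate at 80%.

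**Conclusion.** The concern holds. Sections 16.11 and 16.311 apply a DLT replacement rule to the response endpoint, and nothing elsewhere corrects it. The direction is upward unless removed patients would have responded as often as the others. With assumed removal of 1% to 5%, the false-positive rate at 65% is 0.0995 to 0.109 if no removed patient would have responded, and 0.0986 to 0.1044 if a quarter would have, against 0.097 with no removal. This does not threaten the design. It merits correction because the correction is cheap and because one early failure can decide a result on the cut-off.

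A separate minor point: 16.324 limits adverse-event rates to eligible treated patients, while 13.7 collects data on treated ineligible patients and 16.52 monitors everyone treated at the final dose level. The effect of that difference cannot be sized or signed, and it does not touch the stopping rule or SAE reporting.

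**What to change.** - **13.6:** state that the patient is not evaluable for DLT and is replaced for the DLT assessment only. For consistency, 16.41 to 16.43 should say DLT-evaluable where they count six patients.
- **16.11 and 16.311:** delete the part of the exclusion that refers to 13.6. State that an evaluable patient with no PMR or CMR at the end of cycle 8 is a non-success. Such a patient, if treated at the final dose level, then takes one of the first 25 and 56 places.
- **16.324 (minor):** report adverse-event rates in all patients who received any study treatment, by dose level, so that the final-dose-level set agrees with 16.52.

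The ineligibility and major-violation exclusions are left as they are. The cost is a few sentences, with no change to sample size or cut-offs. The downside is a response rate that may look slightly less favourable, and a lower chance of declaring activity in a trial where a removal actually occurs (0.779 instead of 0.863 at a true 80% with one removal, at the assumed 2%).
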